1. Current or historical evidence of any clinically significant disease or condition, especially cardiovascular or neurological conditions that, in the opinion of the Investigator, may

- increase the risk of exposure to nitrous oxide or complicate the subject's postprocedural course.
- 2. Significant medical conditions or laboratory results that, in the opinion of the Investigator, indicate an increased vulnerability to study drugs and procedures.

Study Procedures:

Potential subjects will be identified as they are scheduled to undergo ECV at the UNC Department of Obstetrics and Gynecology. Subjects will be enrolled in the study by one of the study investigators. Details of the study will be reviewed with potential subjects and those wishing to enroll in the study will be consented for the study by one of the study investigators. Once enrolled participants will be randomized to receive either a mixture of 50% nitrous oxide in 50% oxygen or 100% oxygen, both of which will be delivered via the Nitronox apparatus. Demographic variables will be recorded for each participant at the time they are enrolled in the study (weight, BMI, age, ethnicity, gestational age, parity, placentation, breech position, hx of previous cesarean delivery, hx of previous ECV)

The Nitronox apparatus will be set up to deliver either 50% nitrous oxide in 50% oxygen or 100% oxygen by an anesthesia provider covering labor and delivery who is not involved in the study. The Nitronox device will be covered to prevent participants, study investigators and obstetricians performing the procedure from knowing whether nitrous oxide is being delivered. Nitrous oxide is odorless and colorless, so in that way is indistinguishable from oxygen.

Participants will be prepared for ECV according to current protocols for ECV at UNC. IV access will be obtained and tocolytic agents will be given according to current practice and protocols. Monitoring of maternal and fetal vital signs will be done according to current protocols.

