In addition to the information compiled from the preliminary investigations described above, Chi-square tests of association for the outcome variables of interest and principle predictors will be conducted to reveal important relationships and justifications for more robust analyses.

The primary outcome of the study is pain experienced during ECV. The null hypothesis of this outcome is that there is no difference in pain scores between patients who use a mixture of 50% nitrous oxide and 50% oxygen during ECV (treatment group) compared to those that use oxygen only during ECV (placebo group). Pain scores during each ECV attempt will be recorded for each participant. For those participants who have more than one attempt these scores will be averaged to obtain a single score for the entire procedure. A student t-test will then be performed to evaluate the null hypothesis of no difference in pain scores between the treatment vs placebo groups. A difference in pain score of 2 (Scale: 0-10) is considered clinically significant. Based on a mean pain score difference of 2 and an average standard deviation of 2.5 for the treatment and placebo groups, a statistical power of 80% is expected. Consideration will be given to categorizing the patients into “Low”, “Moderate” and “Severe” pain score categories along clinical guidelines to further assess the impact of analgesia on pain severity. Where feasible, both p-values and confidence intervals for odds ratios from logistic regression and/or parameter estimates from general linear modeling will be reported.

Secondary outcomes of the study include patient anxiety experienced during the ECV procedure, pain scores following the ECV procedure, patient satisfaction with ECV procedure, side effects experienced and OB providers ratings of ease of procedure.

We will be recording whether the ECV procedures are successful and whether any complications occur as a result of the ECV procedure, but given that our study is powered to evaluate patient pain and not these outcomes we do not expect to see any differences. Previous studies have shown that analgesia alone does not alter success rates of ECV, this includes a previous study that used nitrous oxide during ECV.

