Complications of ECV are very rare. Given that nitrous oxide has been demonstrated to be safe for labor analgesia, a similar patient population to ours, we do not anticipate that we would be able to detect any differences in complications in this patient population. These variables are being recorded for completeness.

Several variables known to influence the effectiveness of ECV (BMI, age, ethnicity, gestational age, parity, placentation, type of breech position, amniotic fluid level, tocolytic used, history of prior c-section) are being recorded for each participant. We are also recording whether participants have previously undergone ECV with a prior pregnancy since this could influence their expectations of this procedure. These variables will be analyzed using chi-square or fisher exact test to ensure that there are no differences in these variables between the treatment and placebo groups.

Either a general linear model or a logistic model will be employed to assess the effect of the main effects, interactions, and appropriate covariates on the primary outcomes of interest. Selected covariates and potential confounders will be included in a “forward” regression model and subsequently retained in the final model only if found to explain a significant amount of the variability in the outcome. Candidate covariates include patient anxiety during the ECV procedure, patient satisfaction, ECV success and history of previous ECV.

All data will be recorded during one interaction with the participants and will not require participants to be contacted following the ECV procedure. Because of this the likelihood of missing data and drop out is extremely low.

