The only area where we might expect to have missing data is for delivery information and type of anesthetic used for delivery since not all patients who have an ECV at UNC actually deliver at UNC. However, this data is included on the data sheet only because we are curious to know whether involvement in the study might influence participants to try nitrous oxide for labor analgesia. The use of nitrous oxide for labor, while common worldwide, remains uncommon in the United States. Many women who present in labor have actually never heard of the use of nitrous oxide for labor analgesia. We also have parturients who come to UNC to deliver specifically because we offer nitrous oxide for labor analgesia. It would be interesting to know whether our contact with them through the consent process may inform them of and potentially lead them to consider use of nitrous oxide for labor analgesia.

Power analysis:

A power analysis to determine the sample size required to see a difference in pain score of 2 between the groups was performed which yielded the needed sample size of 50. This analysis

was based on pain scores from previous studies on pain during ECV in the setting of no analgesia as well as use of nitrous oxide or remifentanil for treatment of pain (Burgos et al, Fok et al, Munoz et al).

Normal Distribution $\alpha=0.05$	
Mean Difference	2
Standard Deviation	2.4
Total Sample Size	50
Number of Sides	2
Power	0.823

Lognormal Distribution $\alpha=0.05$	
Group 1 Geometric Mean	4.5
Group 2 Geometric Mean	6.5
Coefficient of Variation	0.45
Total Sample Size	50
Number of Sides	2
Power	0.843

Data handling:

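### Forward selection with unnamed interactions makes the adjusted pain analysis's p-value and confidence interval optimistic, by an amount the plan leaves open; the primary t-test is unaffected

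*Combined protocol and SAP*

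**What the plan says.** All of this is in the section on study outcome evaluation. The primary outcome paragraph tests the null hypothesis on pain with an unadjusted Student t-test, after averaging each woman's scores over her attempts. It adds that, where feasible, "both p-values and confidence intervals for odds ratios from logistic regression and/or parameter estimates from general linear modeling will be reported".

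The covariate modelling paragraph then plans a general linear or logistic model to assess "the effect of the main effects, interactions, and appropriate covariates on the primary outcomes of interest". Covariates and possible confounders go into a forward regression and are "subsequently retained in the final model only if found to explain a significant amount of the variability in the outcome". Four candidates are named: anxiety during the procedure, satisfaction, ECV success and previous ECV. The wording leaves that list open.

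The plan does not give:

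- an entry or retention threshold
- a closed list of candidates
- the interactions to be considered
- a rule that a main effect must precede its interaction
- the coding or centring of covariates
- a statement that arm is always in the model
- any allowance for selection.

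It does not label the model exploratory.

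**The concern.** Forward selection keeps a covariate because it happens to fit these 50 women. The final model is then read as if it had been fixed in advance. Terms chosen for reducing residual variance in the sample make the standard error of the arm effect too small, so the p-value is too low and the interval too narrow.

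Interactions add a second problem. Once an arm-by-covariate product is in the model, the arm coefficient answers a different question unless the covariate is centred. For previous ECV coded 0/1 it is the effect in women with no previous ECV. For a 0-10 rating it is the effect at a rating of zero. Reported as the effect of nitrous oxide, it would mislead.

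The adjusted estimate is likely to be printed beside the t-test on the same outcome. If the two differ, nothing in the plan says how much trust the adjusted one deserves.

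**Working it through.** **Inputs from the documents.** The power analysis gives the total size, "which yielded the needed sample size of 50", with SD 2.4 and a two-sided alpha of 0.05. The target difference is in the primary outcome paragraph: "A difference in pain score of 2 (Scale: 0-10) is considered clinically significant". Study Procedures gives two arms, with women "randomized to receive either a mixture of 50% nitrous oxide in 50% oxygen or 100% oxygen". No allocation ratio is stated, so 1:1 (25 per arm) is assumed.

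**The plan's own figures.** SE = 2.4 × √(2/25) = 0.679. The noncentrality is 2/0.679 = 2.95 on 48 degrees of freedom, which gives power 0.823, as stated. The lognormal row also reproduces (0.843). These figures belong to the t-test. The plan states no error rate for the adjusted model, so there is none to reproduce.

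**How many candidates.** Four are named. The preceding paragraph lists ten variables thought to influence ECV, plus previous ECV, which makes 11. Adding anxiety, satisfaction and ECV success makes 14. The counts of 11 and 14 apply only if the open list is read that widely.

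**Simulation under no treatment effect.** Assumed: 25 per arm, 8,000 trials per setting, linear model, arm always in the model, covariates independent of arm (alternating 0-10 ratings with mean 5 and SD 2.4, and binary items), and forward entry at p<0.05. Either no covariate is related to pain or one explains 30% of its variance; cells show the two cases in that order. The Monte Carlo SE near 5% is √(0.05 × 0.95/8000) = 0.24 percentage points.

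| Terms eligible to enter | 4 candidates | 11 candidates | 14 candidates |
|---|---|---|---|
| Covariates only | 5.4%, 5.5% | 6.0%, 6.5% | 7.0%, 6.6% |
| Plus interactions, main effect first, centred | 5.6%, 5.3% | 6.5%, 6.5% | 6.5%, 6.7% |
| Plus interactions, main effect first, uncentred | 5.6%, 8.0% | 7.6%, 9.3% | 8.2%, 11.1% |
| Plus interactions, no hierarchy, centred | 5.7%, 5.4% | 7.7%, 6.8% | 8.0%, 7.5% |
| Plus interactions, no hierarchy, uncentred | 10.8%, 13.7% | 20.3%, 22.8% | 23.5%, 26.0% |

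Entries are the percentage of trials in which the arm coefficient has p<0.05. In the same runs the unadjusted t-test rejected in 4.6-5.4% of trials. A fixed model with every candidate and no interactions rejected in 4.2-5.5%. Both are nominal within simulation error.

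**Sensitivity to the assumptions.** A separate set of 4,000 trials per setting, with one covariate explaining 10% of variance, gave 5.9% (4 candidates) and 6.8% (11) without interactions. With uncentred interactions free to enter it gave 11% and 16%, and 6.9% and 8.0% if the main effect had to enter first. Smaller runs of 1,200-3,000 trials gave about 5-5.5% for four candidates and 5.5-7% for 11-14, covariates only. A looser entry level of 0.15 with 11-15 candidates, covariates only, gave about 7-9%.

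**Coverage.** With arm always in the model, a constant treatment effect does not alter which covariates are selected. Coverage of the nominal 95% interval is therefore 100% minus the rate shown: 94.5% at a rate of 5.5%, and 74% at a rate of 26%.

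**Why the uncentred rows are high.** Write pain = a + b₁·arm + b₂·X + b₃·arm·X. The arm effect at X = x is b₁ + b₃x, so b₁ is the effect at X = 0 and equals the effect at the mean of X minus b₃ × mean. For a rating with mean 5 and SD 2.4, mean/SD = 2.08, and the correlation between the estimates of b₁ and b₃ is −2.08/√(1 + 2.08²) = −0.90. Selecting the product because b₃ is extreme therefore selects an extreme b₁ as well.

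**The case against.** The strongest reply is that the primary inference is safe. The null hypothesis on pain is assigned to an unadjusted t-test, and nothing says the model replaces it. That stands. A reader might infer that the trial's primary false-positive rate is inflated; the documents do not support that.

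Second, the forward-entry sentence speaks only of covariates and confounders. Interactions appear in the sentence before it, as contents of the model, and are not said to involve arm. That they compete for entry is a reasonable reading but not a stated rule. This stands, and the higher figures depend on it.

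Third, with the four named candidates and no interactions, the excess over 5% is small. The other recorded variables are assigned to balance tests and are not named as model candidates. This also stands, though the open list does not exclude them.

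Fourth, three of the four named candidates (anxiety, satisfaction, ECV success) are observed after the gas has started and may depend on arm. The simulation does not represent that. It is a separate source of bias, and the figures here do not cover it.

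None of this supplies a missing rule, or makes an interval that ignores its own selection valid.

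**Conclusion.** The point holds for the adjusted analysis of pain and goes no further. The plan states a selection rule whose search is ignored in the p-values and intervals to be reported, so these are optimistic.

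The size is about 5-6% against a nominal 5% with the four named candidates, and about 5.5-7% with 11-14. If arm-by-covariate interactions may enter, it runs from about 5% to over 25%. A reader might take one figure from the table, such as 6-7% for covariates only or 11-16% with interactions, as a property of this plan. The documents do not support that, because the result turns on the candidate count, hierarchy and centring, all left unstated. For the same reason 16% is not an upper limit.

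The figures rest on 1:1 allocation, entry at p<0.05, arm always in the model, covariates independent of arm, and the linear version of the model. The statement about covariate = 0 is algebra and needs no simulation, but it applies only if an uncentred interaction is kept. The change is worth making, although the primary test does not depend on it.

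**What to change.** In the covariate modelling paragraph, replace forward selection with one linear model fixed before unblinding. It should contain arm plus a short named list of pre-gas baseline variables that are already collected at enrolment, for example parity and previous ECV. Keep all of them regardless of significance and include no interactions. Report the arm coefficient with its 95% confidence interval as supportive of the t-test.

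If effect modification is of interest, name the arm-by-baseline interaction in advance, show it separately as exploratory, and do not take the arm effect from that model.

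This changes wording only and leaves the t-test, the sample size and data collection as they are. The downside is that a weak covariate stays in the model and costs one degree of freedom. With two such covariates, the residual degrees of freedom fall from 48 to 46.

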Nitrous oxide is an ideal drug for use during ECV. Nitrous oxide provides analgesia, decreases the perception of pain, and has an anxiolytic effect. Some women find nitrous to be a satisfactory and effective agent for analgesia during labor⁶. It has a rapid onset and offset and is noninvasive. Pain during ECV is of relatively short duration, less than 5 minutes, and can easily be anticipated³. Nitrous oxide could be easily self-administered to treat the pain associated with ECV in much the same manner as it is commonly used to treat the pain associated with strong uterine contractions during labor. For these reasons, nitrous oxide may be an appropriate analgesic for patients undergoing ECV.

Worldwide, nitrous oxide is often used for labor analgesia and interest in nitrous oxide use continues to increase in the United States⁶. It has been estimated that nitrous oxide is used by approximately 50% to 75% of laboring women in the United Kingdom, and approximately 60% in Finland. Nitrous oxide is used and widely considered to be safe in many parts of the world including Canada, Australia, and New Zealand⁷. Use in the United States is currently estimated

to be <1% but with rapidly increasing interest. UNC is the third academic institution in the U.S. to offer self-administered inhaled nitrous oxide for labor analgesia.

In the context of obstetric analgesia, “nitrous oxide” refers to a half-and-half combination of oxygen and nitrous oxide gas, called by the trade name “Nitronox” (in the United States) and “Entonox” (in the United Kingdom). It is self-administered by the laboring woman using a face mask. It is generally administered beginning approximately 30 seconds before the onset of a strong contraction until the pain associated with contraction eases⁷. The Nitronox delivery system includes a demand valve which limits delivery of nitrous oxide to the inspiratory phase of ventilation. It also includes a scavenging system that collects expired gasses to minimize environmental exposure.

Nitrous oxide is the only commonly used inhaled labor analgesic in modern obstetric practice and has a long history of safe use. This is likely related to the ease of administration, lack of flammability, absence of pungent odor, minimal toxicity, minimal depression of the cardiovascular system, lack of effect on uterine contractility, and the fact that it does not trigger malignant hyperthermia⁷.

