Immediately before an ECV attempt participants will breathe through the facemask of the Nitronox device for 30 seconds and will then be free to use the device ad lib during the ECV attempt. Immediately following each attempt, while fetal monitoring is occurring, the participants will be asked to rate their maximum pain score (0-10) during the previous attempt. They will also be asked to rate their current level of anxiety (0-10). This process will be repeated for any further ECV attempts.

At conclusion of all ECV attempts, while fetal monitoring is occurring, the participants will be asked to rate their current level of pain (0-10), their satisfaction with the procedure (0-10) and about any side effects they experienced (nausea, vomiting, dizziness, headache, other). Participants will continue to be monitored on labor and delivery as current protocol dictates, typically 30 minutes of maternal and fetal monitoring if there are no complications and fetal status is reassuring.

Following the procedure, the obstetrician who performed the procedure will be asked to rate how difficult they felt it was to perform the procedure (1-10) and to rate how much they felt the analgesic provided assisted in performing the procedure (1-10). They will also be asked to

indicate whether they thought the patient was in the treatment or placebo arm of the study. This will be recorded to address the adequacy of blinding.

Outcomes that will be recorded following the procedure include whether the procedure was successful, the number of attempts performed, complications associated with the procedure (maternal hypotension, fetal bradycardia transient/persistent, emergent cesarean delivery, cord prolapse, placental abruption, other), eventual mode of delivery, indication for cesarean delivery if performed and analgesic/anesthetic used for delivery if any.

All study variables will be assessed and recorded by one of the study investigators to ensure consistency in data collection.

Study outcome evaluation:

A suite of preliminary tabular and graphical investigations will be conducted prior to quantitative analyses to provide a thorough understanding of the data. These investigations will include:

- a. Descriptive statistics, with histograms and boxplots on continuous variables
- b. Frequency distributions on discrete variables
- c. Correlations among potential model predictors and covariates to reveal potential variable multicollinearity problems.

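### Three of the four named covariates for the supplementary pain model are measured after gas exposure, so its adjusted treatment effect is expected to be biased if they are retained; the primary t-test is unaffected

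*Combined protocol and SAP*

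**What the plan says.** All references are to the combined protocol and SAP. Study outcome evaluation assigns the primary hypothesis to an unadjusted test: "A student t-test will then be performed to evaluate the null hypothesis of no difference in pain scores". Where practicable, p-values and confidence intervals are to accompany model results, and "parameter estimates from general linear modeling will be reported".

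Later in the same section, a general linear or logistic model with forward selection is planned for the primary outcome. Covariates and possible confounders stay in the final model only if they explain significant variability in that outcome. The named list is: "Candidate covariates include patient anxiety during the ECV procedure, patient satisfaction, ECV success and history of previous ECV".

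Two of these variables are outcomes elsewhere in the section: "Secondary outcomes of the study include patient anxiety experienced during the ECV procedure, pain scores following the ECV procedure, patient satisfaction with ECV procedure". The Background states: "Nitrous oxide provides analgesia, decreases the perception of pain, and has an anxiolytic effect". It also lists better satisfaction and more successful versions among the potential benefits. On success, Study outcome evaluation points the other way: "Previous studies have shown that analgesia alone does not alter success rates of ECV".

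**The concern.** In a randomised comparison, a variable that arises after treatment starts cannot confound the treatment effect. It can carry part of that effect, or be a consequence of the outcome. Holding it constant removes some of the effect that the trial set out to measure.

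The forward rule makes this more likely. It selects on association with pain and ignores timing, so the variables closest to pain, such as anxiety around the attempt and satisfaction with the procedure, are the likeliest to enter.

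At stake is a second estimate on the primary outcome, with its own p-value and interval, that could contradict a valid t-test. The section does not explicitly rank the two analyses.

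**Working it through.** **Timing of the four candidates (Study Procedures).** Gas starts 30 seconds before each attempt.

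| Candidate | Recorded | Before gas? |
|---|---|---|
| Anxiety | After each attempt | No |
| Satisfaction | After all attempts | No |
| ECV success | After the procedure ("Outcomes that will be recorded following the procedure include whether the procedure was successful") | No |
| History of previous ECV | At enrolment | Yes |

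Three of four follow exposure. No anxiety rating before the gas is described that could stand in.

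**The plan's own power figure.** Inputs from Power analysis: difference 2, SD 2.4, total 50, two-sided alpha 0.05. Equal allocation (25 per arm) is assumed because no ratio is stated. The noncentrality is 2 / (2.4 × √(2/25)) = 2.95 on 48 degrees of freedom. The noncentral t gives power 0.823, as stated. With the SD of 2.5 given in Study outcome evaluation, power is 0.791 against the stated 80%.

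**Bias in the linear model.** Let δ be the true arm effect on pain, r the within-arm correlation of pain with the covariate, and s the arm shift in the covariate in SD units. With one covariate in the model:

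adjusted effect = δ − r × SD × s

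Take δ = −2, SD = 2.4, r = 0.5:

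- No shift (s = 0): −2.00, no bias.
- Shift only through pain (s = r × δ / SD = −0.42): −2 + 0.50 = −1.50.
- Added direct effect on the covariate (s = −0.8): −2 + 0.96 = −1.04.

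For satisfaction both r and s change sign, so the direction of bias is the same. With two covariates that are consequences of pain and both forced in, the effect is δ × (1 − 2r²/(1 + r²)). This is −2 × 0.60 = −1.20 at r = 0.5, and −0.94 at r = 0.6.

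**Forward selection at N = 50.** The documents give no correlations, entry threshold or rule for keeping arm in the model. Assumed: arm always included, entry at p < 0.05, covariates that are consequences of pain, and 4,000 simulated trials per setting.

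| | r = 0.3 | r = 0.5 | r = 0.6 |
|---|---|---|---|
| One covariate: retained | 56% | 97% | 100% |
| One: mean adjusted reduction | 1.85 | 1.50 | 1.28 |
| One: t-test significant, model not | 5% | 16% | 25% |
| Two: mean adjusted reduction | 1.76 | 1.22 | 0.95 |
| Two: t-test significant, model not | 8% | 27% | 37% |

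At r = 0.5 the model is significant in 67% of trials with one covariate and 57% with two; the t-test stays at about 82% throughout. With no treatment shift in the covariate, the mean reduction at r = 0.5 is 1.99. Repeat runs moved the means by at most 0.03 and the percentages by at most 2 points.

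**No effect on pain, direct effect on anxiety.** If gas lowers anxiety by 0.5 SD and leaves pain unchanged, the formula at r = 0.5 gives 0 − 0.5 × 2.4 × (−0.5) = +0.60 (simulated +0.59), so the gas appears to worsen pain. The model is falsely significant in 8% of trials at r = 0.3 and 16% at r = 0.5, against 5% for the t-test.

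ECV success was not simulated.

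**The case against.** The strongest reply is that the confirmatory analysis is untouched. The t-test carries the primary hypothesis, and sample size and power rest on it. That stands, and it limits how serious the point is.

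Other parts also stand:

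- **ECV success.** The plan expects analgesia not to alter it. On that premise, adjusting a linear model for success alone need not bias the effect. The bias argument rests on anxiety and satisfaction, and only anxiety has a direct statement of a drug effect; improved satisfaction is a hope.
- **Magnitude.** It is wholly assumed. At r = 0.2 a single covariate is retained in only 28% of trials and the mean reduction is 1.96.
- **Scope.** The no-shift, no-bias result is for the linear model. In the optional logistic model, adjustment can change the odds ratio even without a shift, because odds ratios are not collapsible.
- **Reporting.** The sentence on reporting model estimates comes before the forward model is described, so the link between them is a reasonable reading, not an explicit one.

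It can also be argued that the model is meant to explain what relates to pain, where variables recorded after exposure are legitimate. The plan does not say so. It speaks of potential confounders and of the primary outcome, which points to an adjusted treatment effect. Nor does the open-ended wording of the list help, since these three variables are named in it.

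**Conclusion.** The concern holds. Followed as written, the modelling paragraph can produce an adjusted arm effect that is not the total effect of randomised nitrous oxide on pain. Where treatment improves anxiety or satisfaction and these track pain, a true benefit is pulled toward zero: under the stated assumptions from 2 points to between 1.85 and 1.28 with one covariate, and between 1.76 and 0.95 with two, for r from 0.3 to 0.6.

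In the linear model there is no bias if treatment does not shift the retained covariate. For ECV success a shift is uncertain, but it remains an outcome after randomisation and is not a confounder. The point should be fixed, although it does not threaten the primary test.

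**What to change.** Delete anxiety during ECV, satisfaction and ECV success from the candidate covariates for the pain model. Limit adjustment to a prespecified set of variables fixed before randomisation and already recorded, such as history of previous ECV, and keep treatment arm in every model. State explicitly that the unadjusted t-test is the primary analysis and ranks above any model. Analyse the three deleted variables as outcomes only, and label any pain model that contains them as exploratory.

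The cost is one or two sentences in Study outcome evaluation. No extra data, participants or procedures are needed, and the sample size of 50 and the t-test's power do not change.
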